While in human infants we are not able to demonstrate a direct relationship between alveolar structure and the physiologic measurement of D_L , we have done so using a murine hyperoxia model of BPD. **Figure 6** illustrates the impaired alveolar development following neonatal hyperoxia for 7 days, while **Figure 7** illustrates the very strong correlations between structural measures of impaired alveolar development (increased mean linear intercept and decreased vessel density) and in-vivo measurements of pulmonary diffusion (DF) prior to sacrifice⁷³. **Therefore, physiologic measurements of pulmonary diffusion provides an excellent in vivo assessment of parenchymal growth and development.**

0.6-0.4-0.2-0.0-0.2-0.0-0.2-0.0-0.2-0.0-0.2-0.0-

Fig. 6. Alveolar development after room air exposure and hyperoxia for 7 days.

Fig.7. Alveolar development after room air exposure and hyperoxia for 7 days.

Airways: Our laboratory also developed the methods to measure FEFs in infants using the raised volume rapid thoracic technique, which provides comparable information about airway function as maneuvers obtained in cooperative older children and adults^{74;75}. We demonstrated that infants with BPD have decreased FEFs compared to infants born full term⁷⁶. In addition, we have also reported that infants born preterm (30-35 weeks) and who didn't require significant respiratory support also have lower FEF₇₅ in the first year of life compared to full term infants, which persisted into the second year of life⁴ (**Figure 8**). These findings demonstrate our ability to assess airway function in infants, and the significant and persistent effect of preterm birth upon airway function.

[figure not shown]

Fig 8. FEF₇₅ were significantly lower in preterm versus term infants when measured in both year 1 and 2 of life.

b3b. Preterm Human Infants treated with any CPAP vs no CPAP in NICU had Higher VA and DL

Using measures of V_A and D_L , we assessed lung growth and development of 48 stable outpatient infants who had been born preterm between 27 and 36 weeks gestational age (GA), but did not develop BPD versus 88 healthy full term infants¹⁵. The preterm infants had a mean GA at birth of 31.7 weeks, and were studied at a mean of 13.7 months of age. Term infants had a GA of 39.3 weeks and were studied at an average of 14.4

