months. V_A and D_L were not associated with GA, mechanical ventilation or oxygen therapy suggesting that in the absence of extreme prematurity and BPD, prematurity itself does not impair lung parenchymal development. However, further analysis of the preterm infants demonstrated that both V_A and D_L were significantly higher (by about 16%) for infants who received any CPAP in the NICU compared to those who had not received any CPAP (Table 1). This was not a controlled trial of CPAP, but our findings suggest that mechanical stretch from CPAP in preterm infants may produce larger, more functional lungs.

Table 1. V_A and D_L in Healthy Preterm Infants According to CPAP Treatment

Lung Function Measures	No CPAP (n=29)	CPAP (n=19)	P value	% difference
V _A (mL)	606.8 ± 171.5	694.6± 205.2	0.046	16%
D _L (mL/min/mmHg)	3.86 ± 0.97	4.49± 1.42	0.007	16%

Values are Mean ± SD; p values adjusted for length and gender

b3c. Pilot Study: The Effect of eCPAP on FRC through NICU discharge, a RCT

We recently published a pilot study randomizing stable preterm infants \leq 32 weeks of gestation at birth and requiring \geq 24 hours of CPAP for respiratory distress to 2 extra weeks of CPAP (eCPAP) versus CPAP discontinuation when CPAP stability criteria were met¹⁶. CPAP stability criteria included: on CPAP of 4-5 cm H₂O; on room air; respiratory rate \leq 70 breaths/minute, retraction score \leq 1; < 3 self resolving apneas (< 20 seconds) and/or bradycardia (< 100 bpm) and/or desaturations (pulse oximeter oxygen saturation, SpO2 <86%) in 1 hour for past 6 hours; average SpO2 >86% for 90% of the time over the past 24 hours, not being treated for a PDA or sepsis, and tolerating time off CPAP during routine care (up to 15 minutes).

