
j. Removal of Patients from Allocated Treatment Arm or from the Study

The investigator or the parents of the preterm infant may discontinue treatment arm allocation or withdraw the infant early from the study at any time for safety or administrative issues. The infant may be withdrawn from the treatment arm per parent request, protocol violation, worsening clinical condition, or investigator decision. Infants who discontinue study arm/treatment allocation will remain in the study for outcome measurements, unless the consent is withdrawn.

6. Study Procedures Involved

a. Clinical Data Collection in NICU

Pertinent maternal and infant data through discharge from the NICU will be collected, including: maternal: age; parity; smoking history; antenatal steroid treatment; etiology of preterm delivery; birth weight and gestational age; surfactant dosing; duration of: oxygen, mechanical ventilation and CPAP (prior to study randomization); respiratory medications; gestational age at full nipple feeds and at discharge.

During the 2-week treatment period detailed data will include daily weights; weekly lengths; calories per day; apneic episodes; oxygenation needs; parental interactions; developmental interactions such as frequency and duration of time spent skin to skin with a parent.

In addition, downloads of continuous oxygen saturation will be done during the two week treatment period with a separate pulse oximeter (will not be used for clinical care so monitor will be covered from caretaker and alarms disabled) with a 2 second averaging time and a 2 second sample rate (Radical; Masimo Corp., Irvine, California) monitors. Intermittent hypoxemia (IH) events will be defined as an oxygen saturation \leq 80% for \geq 20 seconds and \leq 180 seconds as previously described⁷⁸⁻⁸⁰. Episodes of IH and other patterns of oxygen saturation will be compared between the groups.

b. Blood for Epigenetics and Proteomics

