General linear mixed models (GLMMs) will be used to compare the primary outcomes of alveolar volume (V_A) between the eCPAP and dCPAP while adjusting for the design factor gestational age at delivery (28 and 6/7 and 29 and 0/7 weeks) and other baseline variables that are found to be statistically different between the two groups. Since the lung function measures are highly dependent on infant length and sex, we will further adjust for length and sex in the GLMMs. In order to adjust for intra-twin correlations, generalized Estimating Equations (GEEs) with the linear link function will be used to model $V_{A...}$ The GLMMs can be performed using the GEE estimation approach. Intention to treat analysis will be used for all aims as the primary analysis. The intention to treat population is defined as all randomized infants and the analysis uses the assigned randomization group even if infants did not complete the intervention. In addition, a per protocol analysis will be completed for all aims. The per protocol population is defined as all infants who successfully completed the treatment arm to which they were assigned.

b2. Specific Aim 2 (Secondary Outcomes)

Lung diffusion (D_L) and FEF₅₀ will be will be analyzed with the same general approaches described for the primary outcome in SA #1.

b3. Specific Aim 3 (Exploratory Outcomes)

Logistic regression models will be used to compare the incidence of wheeze and the incidence of wheeze and cough between the two groups adjusting for GA at delivery (<29 vs ≥ 29 weeks). Neurodevelopmental scores will be analyzed with the same general approaches described for the primary outcome in Specific Aim 1.

c. Missing Data

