Specific Aim 1 (Primary Outcome): General linear mixed models (GLMMs) models will be used to compare the primary outcome of alveolar volume (V_A) between the eCPAP and CPAP discontinuation group while adjusting for gestational age at delivery (randomization stratification variable) and other baseline variables that are found to be statistically different between the two groups. Since the lung function measures are highly dependent on infant length and sex, we will further adjust for length and sex in the GLMMs as indicated. In order to adjust for intra-twin correlations, generalized estimating equations (GEEs) with the linear link function will be used to model V_A . The GLMMs can be performed using the GEE estimation approach. Intention to treat analysis will be used for the primary analysis of all aims.

Specific Aim 2 (Secondary Outcomes): Lung diffusion capacity (DLCO) and forced expiratory flows (FEFs) and specifically FEF $_{50}$ will be analyzed with the same general approaches described for the primary outcome of V_A in Specific Aim 1.

FRC measurements in the NICU done pre and post randomization and FEF₂₅₋₇₅, FEF₇₅ done at 6 months of corrected age will be analyzed with the same general approaches as above in Specific Aim 1.

Specific Aim 3 (Exploratory Outcomes): Logistic regression models will be used to compare the incidence of wheeze and the incidence of wheeze and cough between the two groups adjusting for gestational age at delivery (See appendix for standardized respiratory questionnaire administered). Neurodevelopmental scores will be analyzed with the same general approaches described for the primary outcome of V_A in Specific Aim 1.

Intention to treat analysis will be used for the primary analysis of all aims. In addition, all of the aims will also be analyzed with the same general approach using a per protocol analysis and "as treated analysis".

Sample Size and Power Considerations. No studies have compared V_A at 6 months of age in stable infants randomized to eCPAP versus CPAP discontinuation in the NICU. Data from our pilot eCPAP study showed a 12% higher FRC in infants randomized to eCPAP at the end of two week treatment period¹. A study by [name] et al reported a 16% difference in both V_A and D_L in preterm infants according to CPAP treatment in the NICU (Table 1)² and a 12% difference in D_L between infants with BPD versus healthy term infants³. Therefore,

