we powered our randomized trial to detect a 12% difference in V_A between the eCPAP and CPAP discontinuation groups.

Using ANCOVA model and assuming a mean V_A of 642 mL (SD=189) based on data of the overall mean and SD from the

Table 1. Estimated power for 34 infants per group with completed PFT data

Macan (SD) in _____ Estimated Power for Group Differences

Outcome Measures	Mean (SD) in Control Group	Estimated Power for Group Differences		
		12%	15%	17%
Alveolar volume (V _A)	642 (189)	80	92	97
Lung diffusing capacity (D _L)	4.1 (1.19)	80	92	98
Forced Expiratory Flow (FEF ₅₀)	346 (129)	35	49	60

control and CPAP groups reported in Assaf et al², a sample size of 34 infants per group is needed to yield 80% power for detecting a 12% difference (effect size=0.42) in V_A in the eCPAP group at α =0.05. This sample size also allows us to detect a 12% difference in D_L with an effect size of 0.42. We estimate that 18% of the study patients will be twin pairs based on our pilot eCPAP study. Conservatively counting just one infant out of each twin pair for sample size estimation, we will need 38 infants per group (76 total infants at 6 months) with completed V_A outcomes. We further assume a 10% missing data in the NICU (unsuccessful test or infants transferred to another facility) and a 15% loss from NICU discharge to the 6 month PFT (cohort loss, unacceptable PFT, unsuccessful sedation) and therefore we will need to randomize and/or assign 50 infants per group (total n=100) into the trial. This sample size will provide 80% power for detecting an effect size difference of 0.42 in outcome measures between the two groups in Aim 1 (primary outcome of V_A) and Aim 2 for D_L . This sample size allows us to detect a 23% difference in FEF₅₀.

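### The SAP makes the length and sex adjustment of the primary V_A model conditional without a criterion, neither document says which length is used, and the stated 80% power cannot be tied to any defined model

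*SAP*

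**What the plan says.** **Length and sex.** Protocol section 7 b1 says "we will further adjust for length and sex in the GLMMs", with no condition. The SAP under Specific Aim 1 repeats the sentence with a qualifier: "we will further adjust for length and sex in the GLMMs as indicated". Both give the same reason, that lung function depends strongly on length and sex. The SAP applies the same approach to DLCO and FEF50 under Specific Aim 2.

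**Which length.** Protocol section 6a schedules "daily weights; weekly lengths; calories per day" during the 2-week treatment period. No length is listed for the 6-month test in protocol section 6d or Appendix A, and neither analysis section names a time point.

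**Other covariates.** Gestational age at delivery, the stratification factor, always enters. Beyond that, both documents add "other baseline variables that are found to be statistically different between the two groups".

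**Power.** Protocol section 7a and the SAP's Sample Size and Power Considerations assume an ANCOVA, a mean V_A of 642 mL, SD 189, a 12% difference (effect size given as 0.42) and alpha 0.05, and conclude that "a sample size of 34 infants per group is needed to yield 80% power". Neither states the covariates, the R² or whether the test is one- or two-sided. SAP Table 1, "Estimated power for 34 infants per group with completed PFT data", has rows for V_A, D_L and FEF50.

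**Age window for the V_A test.** Protocol section 6d gives 5–8 months corrected age; the SAP's Population section gives 4–12 months.

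**The concern.** The two documents do not fix the same primary model. Under the protocol, length and sex are always in. Under the SAP they may be in or out, and nothing says what would indicate them or who decides. The SAP's own reason for adjusting leaves no evident purpose for a condition.

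The choice of length is also open. A NICU length and a length at the 6-month test are different covariates, months apart. The first should explain less of V_A at 6 months. The second is measured after randomisation, so using it changes what effect is estimated.

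The significance rule for other covariates picks variables because they happen to differ between randomised arms rather than because they predict V_A. The covariate list is then unknown until the data are seen.

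At stake are a fully specified primary analysis and the basis of the 80% power. Length and sex are the only predictors that the documents call strong, so they are presumably what the ANCOVA relies on. That is an inference, because the power section names no covariates.

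**Working it through.** **1. The plan's own inputs.** Protocol section 2 b3b, Table 1, gives V_A 606.8 ± 171.5 (n=29) and 694.6 ± 205.2 (n=19). The overall mean is (29×606.8 + 19×694.6)/48 = 641.6 and the overall SD is 188.5, so 642 and 189 reproduce. The difference is 0.12×642 = 77.04 mL, and 77.04/189 = 0.408 (stated 0.42). The loss step reproduces: 76/(0.90×0.85) = 99.3, stated 100.

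**2. The 34 per group does not follow from the printed inputs alone.** With no covariate gain and the normal approximation, n = 2(z_α + z_β)²/d²:
- two-sided: 2(1.960+0.842)²/0.408² → 95 per group
- one-sided: 2(1.645+0.842)²/0.408² → 75 per group

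**3. Power at 34 per group by R².** Noncentral t with noncentrality d/√(1−R²) × √(n/2). Degrees of freedom are 2n−2, less 3 (stratum, sex, length) when R² > 0. At R² = 0 the noncentrality is 0.408×√17 = 1.68; at R² = 0.65 it is 1.68/√0.35 = 2.84.

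| R² (assumed) | two-sided | one-sided |
|---|---|---|
| 0 | 38% | 51% |
| 0.25 | 48% | 61% |
| 0.39 | 56% | 69% |
| 0.50 | 65% | 76% |
| 0.65 | 80% | 88% |

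The R² needed for 80% is 0.65 (two-sided) or 0.55 (one-sided) at d = 0.408, and 0.63 or 0.53 at d = 0.42. On the most favourable printed figures, 38 per group and d = 0.42, the noncentrality without covariate gain is 0.42×√19 = 1.83 and power is 44% or 57%.

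**4. R² that reproduces each row of SAP Table 1** (34 per group; columns at 12/15/17%):

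| Row | stated power | R², two-sided | R², one-sided |
|---|---|---|---|
| V_A | 80/92/97 | 0.65/0.62/0.63 | 0.55/0.54/0.55 |
| D_L | 80/92/98 | 0.64/0.61/0.65 | 0.54/0.52/0.58 |
| FEF50 | 35/49/60 | 0.31/0.29/0.30 | about 0 (−0.09/−0.03/0.04) |

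V_A and D_L are consistent with one R²; FEF50 is not. Different outcomes may well have different R², but then each needs stating.

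**5. Can protocol Table 1 supply the R²?** Its note reads "p values adjusted for length and gender". For V_A the pooled SE is 54.7, so t = 87.8/54.7 = 1.60 and the unadjusted p is 0.115 (df 46), against a printed adjusted p of 0.046. With t = 2.05 at p = 0.046 (df 44), adjusted SE = adjusted difference/2.05 and R² = 1 − (adjusted SE/54.7)². This assumes no overlap between CPAP group and covariates. The adjusted difference is not printed:

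| Assumed adjusted difference (mL) | implied R² |
|---|---|
| 97 (16% of 606.8) | 0.25 |
| 87.8 (crude difference) | 0.39 |
| 80 | 0.49 |
| 70 | 0.61 |
| 67 | 0.64 |

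The range runs from well below the needed value to about equal to it, so the table does not settle the question.

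**6. The significance rule.** If 5 or 10 independent baseline variables are tested at 5% (assumed numbers), at least one enters by chance with probability 1−0.95⁵ = 23% or 1−0.95¹⁰ = 40%. In simulations with length and sex always in the model and assumed sets of further candidate covariates, the rule moved power by about −2 to +1 points and left type I error at 4–5%.

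**The case against.** The best defence is that the analysis is less open than it looks. The SAP still says that it will adjust, gestational age always enters, and the statistician is blinded to allocation, so the qualifier gives little room for a result-driven choice. The stated reason for adjusting, and the length-adjusted outpatient data in protocol section 2 b3b, point to length at the test. Appendix A is not exhaustive: it also omits the 6-month finger-stick haemoglobin, which section 6d plans. Section 6d refers operating procedures to a manual that is not among the documents. All of this stands. It makes length at test the likely intention, but it does not write the model down.

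On power, 34 per group counts one infant per twin pair, while the GEE would use both. At 38 per group with effect size 0.42, treating twins as independent (an upper bound), an R² of 0.60 gives 82% two-sided and 89% one-sided. That also stands: 80% is attainable if R² is high enough.

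A reader might infer from protocol Table 1 that V_A power misses 80% even with full adjustment. The documents do not support this. The adjusted difference is unreported, and the data are from 48 non-randomised infants who "were studied at a mean of 13.7 months of age". A reader might also put a figure on the power lost by using a NICU length; that would need a correlation between NICU and 6-month length that no document gives.

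**Conclusion.** The point holds as a specification gap with a real consequence for power. The SAP conditions an adjustment that the protocol makes unconditional, the length is unidentified, and the 80% cannot be traced to a defined model. The size is the distance between 38% (two-sided) or 51% (one-sided) with no covariate gain and the stated 80%, which requires R² of about 0.63–0.65 or 0.53–0.55. These figures rest on the printed mean, SD, difference and 34 per group, with R² acting only through the residual variance.

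The 38% should not be read as the expected power: it applies only if covariates explain nothing, and at least gestational age enters. Nor do the figures show that 34 per group is wrong; they show that the inputs behind it are incomplete. The significance rule is poor practice in both documents, but its numerical effect is small. The mismatch in age windows is minor. It bears on the choice of length because, as protocol section 2a notes, lung volume grows quickly in the first two years.

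**What to change.** Before unblinding:

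1. Delete the qualifier *as indicated* from the SAP, and the significance rule for other covariates from both documents.
2. For V_A, DLCO and FEF50, always include gestational-age stratum, sex and length measured at the 6-month PFT. Name any further baseline covariate now, on prognostic grounds.
3. Because length at test is post-randomisation, report it by arm and add a sensitivity analysis without it.
4. State the covariates, R² and sidedness behind each power row, and restate the power if that R² cannot be supported.
5. Minor: reconcile the 5–8 and 4–12 month windows for V_A.

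**Cost.** Mostly wording. The three covariates use three degrees of freedom that the protocol's model already spends. If length is not already recorded at the 6-month test, it is one measurement at an existing visit.

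**Downsides.** Adjusting for length at test could absorb part of any treatment effect on growth. The sensitivity analysis without length will have low power (38% two-sided or 51% one-sided at 34 per group if the remaining covariates explain nothing). Restating the power may show that a 12% difference is not detectable at 80%.

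### The primary V_A test is named as both a mixed model and a GEE, with no variance method; a GEE with the usual uncorrected sandwich errors would run at about 6-7%, not 5%

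*SAP*

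**What the plan says.** The SAP, under Specific Aim 1, opens with "General linear mixed models (GLMMs) models will be used to compare the primary outcome of alveolar volume (V_A"). The model adjusts for gestational age at delivery, for length and sex, and for any baseline variable that differs significantly between arms. To handle correlation between twins it then says "generalized estimating equations (GEEs) with the linear link function will be used to model V_A", and closes with "The GLMMs can be performed using the GEE estimation approach". Protocol section 7.b1 gives the same sequence and ends on the same sentence.

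Neither document states a random effect, working correlation, variance estimator, reference distribution, degrees of freedom or small-sample correction. SAS 9.4 is named, but no procedure or option.

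The significance level appears only in the sample-size text: "in V_A in the eCPAP group at α =0.05". The same text gives the size of the analysis set, "we will need 38 infants per group (76 total infants at 6 months"), and the twin share: "We estimate that 18% of the study patients will be twin pairs based on our pilot eCPAP study". Twins go to the same arm (protocol 5.h; SAP Population, footnote 1). The SAP applies the Aim 1 approach to DLCO, FEF50, other flow measures, FRC and the neurodevelopmental scores.

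**The concern.** A linear mixed model takes its standard error from a likelihood with a random family effect. A GEE uses a working correlation and, by custom, a sandwich variance. With many clusters the two give nearly the same answer. With few they need not, because an uncorrected sandwich built from fitted residuals tends to be too small, more so as covariates are added. A normal reference makes this worse.

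Treatment varies only between families here, so the number of families governs the test. The covariate list is open-ended. The plan therefore permits analyses of the same comparison that differ in their true error rate, and the trial's conclusion rests on that one test. Blinding the statistician neither settles which analysis is primary nor repairs a standard error that is too small.

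**Working it through.** **1. The plan's own numbers.** The SAP says "a sample size of 34 infants per group is needed to yield 80% power for detecting a 12% difference (effect size=0.42"), "assuming a mean V_A of 642 mL (SD=189").

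- Twin step: with 18% of infants in pairs, families number 1 - 0.18/2 = 0.91 of infants. 34/0.91 = 37.4, rounded up to 38 per group. This reproduces.
- Loss step: 38/(0.90 × 0.85) = 49.7, rounded up to 50 per group. This reproduces.
- Power step: without covariate adjustment, two-sided power at effect size 0.42 is Φ(0.42 × √(34/2) - 1.96) = 41%. Reaching 80% needs the ANCOVA covariates to explain about 62-64% of the variance, a figure the documents do not give. This is a separate point and does not bear on type I error.

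**2. Number of clusters.** 76 × 0.18/2 = 6.8, so about 7 twin pairs and 76 - 7 = 69 families. The plan's own count of independent units is nearly the same: 2 × 34 = 68.

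**3. Parameters.** Intercept, arm, gestational-age stratum, length and sex make five, plus an unknown number of imbalance-selected covariates.

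**4. Simulation under no effect.** There were 7 pairs and 62 singletons, twins in the same arm, and blocks of 2 or 4 within strata. Errors were normal and residual twin correlation ran from 0 to 0.8. Each GEE setting had 10,000-40,000 replicates (Monte Carlo error about 0.1-0.3 points) and each mixed-model setting 6,000. The level is taken as two-sided, which the documents do not state. Rejection rates at nominal 5%:

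| Analysis | Named covariates | 2 added | 4 added |
|---|---|---|---|
| GEE, independence, uncorrected sandwich, normal reference | 6.3-6.8% | 7.2-7.5% | 7.3-8.0% |
| GEE, exchangeable, uncorrected sandwich, normal reference | 6.1-7.7% | 7.3-8.6% | 7.6-8.7% |
| GEE, exchangeable, Mancl-DeRouen sandwich, t reference | 4.0-4.6% | 4.2-4.5% | 3.9-4.4% |
| REML mixed model, random family intercept, t reference | 4.9-5.1% | 4.5-5.4% | not run |

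The 7.7% in the second row arises at zero twin correlation; at 0.3-0.8 the range is 6.1-6.3%. The highest rate in any setting was 8.9% (exchangeable, zero correlation, one added covariate). A separate independence-GEE run gave 6.2% with the named covariates, 6.9-7.1% with one or two added and 7.7% with four.

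**5. Sensitivity.**
- If 18% means the share of families that are twin pairs, there are about 64 families, and the uncorrected test with the normal reference gives 6.0-6.9%.
- If all 100 infants were analysed (100 - 9 = 91 families), it gives 6.1-6.2%.
- Changing only the reference to t, with the sandwich uncorrected, gives 5.3-8.4%, so the t reference alone is not a reliable cure.

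**6. Effect on the interval.** If a test rejects at rate a when 5% is intended, its standard error is short by the factor 1.960/z(1 - a/2).

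- a = 6.2%: 1.960/1.866 = 1.05
- a = 7.1%: 1.960/1.805 = 1.09
- a = 7.7%: 1.960/1.768 = 1.11

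A correctly sized interval is therefore roughly 5-10% wider.

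**The case against.** The strongest reply is that the documents never mention a sandwich variance or a normal reference, and the linking sentence is permissive. A reader might infer that the plan commits to a test running at 6.5-8%, or that the primary p-value will be too optimistic. The text does not support that. The mixed model, which is named first, holds about 5%, so the inflation belongs to one permitted branch.

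The reply is also right on size. The upper end needs added covariates. Protocol section 6.a lists roughly a dozen pre-randomization characteristics. If 12 were independent, the chance that four or more differ at the 5% level is about 0.2% (0.6% for 15), though correlation among them would raise it. The 69 families also reflect losses that protocol section 7.c expects to be overestimated, although the 91-family result shows that full retention does not remove the excess.

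Two further points stand. With an identity link both models target the same mean difference. And a mixed model is not clearly better: V_A may be measured anywhere from 4 to 12 months corrected age, so unequal variance is plausible. Robust errors guard against that and model-based errors do not; this was not simulated.

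The reply does not remove the gap. The SAP says outright that GEEs will be used to model V_A, and a GEE run in its ordinary form exceeds the stated level even with only the named covariates.

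**Conclusion.** The concern holds in conditional form. What is certain is that the primary test carries two names and has no stated variance estimator, reference distribution or small-sample correction. What is conditional is the consequence: a GEE with an uncorrected sandwich and normal reference on about 69 families has type I error of about 6-7% with arm, stratum, length and sex, and about 7-8% if several covariates are added. A mixed model with a t reference stays near 5%.

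The excess is mild, about one to two percentage points with the covariates the plan names. It affects the standard error, interval and p-value only. The figures assume normal errors, a residual twin correlation between 0 and 0.8, a two-sided test and a given number of added covariates; none of these is in the documents. The gap should be closed before the data are analysed.

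**What to change.** Name one primary estimator for V_A in the SAP, with its variance and reference distribution. Either would do:

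- a GEE with identity link, family as cluster, a stated working correlation, a bias-corrected sandwich variance (for example Mancl-DeRouen) and a t reference; or
- a REML linear mixed model with a random family intercept and small-sample degrees of freedom. The simulation used families minus parameters; Kenward-Roger is a natural choice but was not itself simulated.

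Apply the same choice to DLCO, FEF50 and the Bayley scores, which inherit the Aim 1 approach.

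The cost is one SAP sentence and a software setting, with no change to conduct, data or sample size. The interval will be roughly 5-10% wider than with the uncorrected sandwich. The corrected GEE can be slightly conservative, rejecting at about 4%, so a little power is given up.
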